7.4.2.1 Clinical Adverse Events

All summary analyses of AEs and SAEs will be based on the principle of treatment emergence assuming this information is available. For the Montelukast /placebo safety analysis population, an event is considered to be treatment emergent if the onset is after the start of the Montelukast /placebo treatment or the event was present before and subsequently worsened after the Montelukast /placebo start date. For the DMF safety analysis population, an event is considered to be treatment emergent if the onset is on or after the first DMF dose date or the event was present before and subsequently worsened on or after the first DMF dose date.

[figure not shown]
The Medical Dictionary for Regulatory Activities (MedDRA) version 19.1 will be utilized to code and group AEs by System Organ Class (SOC) and Preferred Term (PT). Incidence of AEs and SAEs will be summarized and presented by SOC and PT. Summary analysis of adverse events will be provided. The summaries will include the following numbers and percentages of subjects: in the safety analysis population; with a serious adverse event (SAE); with an AE leading to discontinuation of treatment; and with an AE leading to withdrawal from the study.

The incidence of AEs by relationship to DMF or Montelukast will be summarized by SOC and PT. For a given SOC or PT, a subject with multiple AEs with the different relatedness will be counted once in the most related category.

The incidence of AEs leading to study treatment discontinuation and study withdrawal by severity will be summarized by SOC and PT using severity categories (mild, moderate, and severe). For a given SOC or PT, subjects with multiple AEs with the different severity will be counted once in the category of worst severity.

Deaths that occur will be described in detail in patient narratives. A listing of deaths will also be provided. While the number of deaths is expected to be small, tabulation will be performed if appropriate.

7.4.2.2 Clinical Laboratory Data

8 LIST OF TABLES

The following list of tables includes main tables for the analyses described in the SAP. Other tables may be added.

Table 1: Summary of accounting of subjects

Table 2: Summary of demography

Table 3: Summary of alcohol consumption and tobacco use

Table 4: Summary of medical history

Table 5: Summary of MS disease history

Table 6: Summary of prior disease-modifying MS treatment history

 Table 7: Summary of time on study treatment

Table 8: Summary of time on DMF treatment

Table 9: Summary of time on study

Table 10.1: Number of doses of study treatment taken between Day 0 and Day 10

Table 10.2: Number of doses of DMF treatment taken between Day 0 and Day 10

Table 11.1: Summary of GSRS compliance rate

Table 11.2: Summary of study treatment compliance rate

Table 11.3: Summary of DMF compliance rate from randomization visit to Week 10

Table 11.4: Summary of DMF compliance rate from Day 0 to Day 10 and to Week 10

Table 11.5: Summary of DMF compliance rate from randomization visit to Day 0

Table 12: Summary of concomitant medications

Table 13: Summary of primary endpoint

Table 14: Summary of primary endpoint among patients with GSRS e-Diary compliance rate $\geq 80\%$, at least 5 doses of study medication, and at least 10 doses of DMF in the Day 0 – Day 10 period

Table 15.1: Summary of average change of GI severity score from baseline (Day 0) by ANCOVA, Day 1 to Day 10: overall and by dimension

Table 15.2: Summary of average change of GI severity score from baseline (Day 0) by ANCOVA with additional covariates, Day 1 to Day 10: overall and by dimension

Table 16: Summary of average change of GI severity score from baseline (Day 0) by repeated measures analysis, Day 1 to Day 10: overall and by dimension

Table 17: Summary of average change of GI severity score from baseline (Day 0) by ANCOVA, Day 1 to Day 10, among patients with GSRS e-Diary compliance rate \geq = 80%, at least 5 doses of study medication, and at least 10 doses of DMF in the Day 0 – Day 10 period Table 18: Summary of average change of GI severity score from baseline (Day 0) by repeated measures analysis, Day 1 to Week 10: overall and by dimension

Table 19: Summary of time to first worsening in GSRS score

Table 20: Summary of time to recovery to Day 0 GSRS score from the last occurrence of worst post-baseline GSRS score

Table 21: Summary of average change of GSRS score from baseline (Day 0) by repeated measures analysis, Day 1 to Weeks 1-8

Table 22: Summary of average change of GSRS score from baseline (Day 0) by repeated measures analysis, at 72 hours from the initiation of randomized study treatment (Day 1 - Day 3)

Table 23: Summary of primary endpoint by baseline demographic and disease characteristics

Table 24: Summary of average change of GI severity score from baseline (Day 0), repeated measures analysis, Day 1 to Day 10, by baseline demographic and disease characteristics

Table 25: Summary of average change of GI severity score from baseline (Day 0), repeated measures analysis, Day 1 to Week 10, by baseline demographic and disease characteristics

Table 26: Summary of proportion of subjects who take GI symptomatic therapy during the study

Table 27: Summary of proportion of subjects who discontinue DMF therapy due to GI-related adverse events from Day 0 to Week 10

Table 28: Summary of proportion of subjects who experience flushing events

Table 29: Summary of biomarker scores, changes and percent changes from Tecfidera baseline, by treatment group and visit, DMF safety analysis population

Table 30: Summary of biomarker scores, changes and percent changes from Montelukast baseline, by treatment group and visit, Montelukast/placebo safety analysis population

Table 31.1: Summary of selected hematology parameters, change and percent change from Montelukast baseline, by treatment group and visit, Montelukast/placebo safety analysis population

Table 31.2: Summary of selected hematology parameters, change and percent change from Tecfidera baseline, by treatment group and visit, DMF safety analysis population

Table 32.1: Summary of hematology abnormalities by CTC grades, by treatment group and visit, DMF safety analysis population

Table 32.2: Summary of hematology abnormalities by CTC grades, by treatment group and visit, Montelukast /placebo safety analysis population

Table 33.1: Incidence of adverse events by system organ class and preferred term, Montelukast/placebo safety analysis population

Table 33.2: Incidence of adverse events by system organ class and preferred term, DMF safety analysis population

Table 34.1: Incidence of serious adverse events by system organ class and preferred term, Montelukast/placebo safety analysis population

Table 34.2: Incidence of serious adverse events by system organ class and preferred term, DMF safety analysis population

Table 35.1: Incidence of adverse events leading to the study treatment discontinuation by system organ class and preferred term, Montelukast/placebo safety analysis population

Table 35.2: Incidence of adverse events leading to DMF discontinuation by system organ class and preferred term, DMF safety analysis population

Table 36.1: Incidence of adverse events leading to study withdrawal by system organ class and preferred term, Montelukast/placebo safety analysis population

Table 36.2: Incidence of adverse events leading to study withdrawal by system organ class and preferred term, DMF safety analysis population

Table 37: Incidence of adverse events by system organ class, preferred term and severity, DMF safety analysis population

Table 38: Incidence of adverse events by system organ class, preferred term and by relationship to the study treatment or DMF, DMF safety population

Supporting tables for Figures 1, 2, 5 and 6:

Table P1: Summary of change in GSRS score from baseline (Day 0) by repeated measures analysis, Day 1 to Day 10

Table P2: Summary of change in GSRS score from baseline (Day 0) by repeated measures analysis, Week 1 to Week 10

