6.2.3. Exploratory Endpoints

7. STUDY DESIGN

7.1. Study Overview

This multicenter study will evaluate the effect of montelukast on GI tolerability with relapsing forms of MS treated with DMF at approximately 50 study sites in the US. It is expected that approximately 295 subjects will be initially randomized to obtain approximately 118 subjects dosed with randomized study treatment (59 subjects dosed with randomized study treatment per treatment arm). Not all randomized subjects will be eligible to be dosed with randomized study treatment. Randomized subjects will be required to reach a predefined threshold of GI symptom severity before dosing with randomized study treatment will be initiated. Subjects who withdraw from the study after initiating randomized study treatment will not be replaced.

Subjects will enter a 2-week (+14 days) Screening Period and record pertinent information regarding GI-related events to allow characterization of background GI-related events using the eDiary. Subjects will be required to be \geq 75% compliant in the 14 days prior to randomization to remain eligible to participate in the study. Subsequently, eligible subjects will initially take DMF (120 mg twice daily orally for the first week, 240 mg twice daily orally thereafter) for up to 28 days (DMF-GI Monitoring Period) and record GI-related events in the eDiary. During this period, subjects will take DMF, GSRS scores will be monitored, and subjects who reach a specific threshold will receive an alert through the eDiary to start taking randomized study treatment (10 mg once daily montelukast or placebo) the same day in accordance with the prescribing and labeling information. Subjects who do not meet the threshold or do not demonstrate \geq 75% compliance with the eDiary in the 14 days prior to randomization will be discontinued. Subjects will also use the eDiary to record DMF dosing, randomized study medication dosing, and any symptomatic concomitant medications/procedures. Eligible subjects will return to the study site at Weeks 0, 2, 4, 8 and at Week 10 for evaluation by study site staff. Weeks 2, 4, and 8 will have a visit window of ± 2 days, and Week 10 will have a visit window of \pm 3 days. If more convenient for the subject, visits at Weeks 2, and 8 may be performed remotely by a contracted home health nurse. The Safety Follow-Up Telephone Interview will be conducted 2 weeks (±5 days) after the Week 10 study visit or date of the Early Termination (ET) Visit.

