9.2. Randomization of Subjects

Subjects must be consented before any screening baseline tests or assessments are performed. At the time of consent, the subject will be registered into the study. Participating study sites are required to document all registered candidates initially considered for randomization in the study. If the subject is not randomized in the study, the reasons will be documented in the subject's source documents and on the registration log.

Subjects will be randomized at the Randomization Visit. At this visit, eligible subjects will be randomized to 1 of 2 treatment arms (DMF + montelukast or DMF + placebo) in a 1:1 ratio. Subjects will be instructed not to take the blinded randomized study treatment until they receive an alert through their eDiary. This alert will appear if a subject meets the criteria of GSRS score of ≥ 3 in 1 question for 1 day or a GSRS score of ≥ 2 in 1 question for 2 consecutive days.

No subjects may begin treatment prior to randomization and assignment of a unique subject identification number. Any subject identification numbers that are assigned will not be reused, even if the subject does not receive treatment. Subject identification numbers will be assigned by the Interactive Voice and Web Response System (IXRS).

Refer to the Study Reference Manual for details on registration.

As confirmation, Biogen will provide the Investigator with verification of the subject's registration.

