7.3.5 Analysis methods-Exploratory endpoints

7.4 Safety Data

7.4.1 Safety analysis Population

The primary safety analysis population is the Montelukast/placebo safety analysis population. Selected analyses will also be summarized in the DMF safety analysis population.

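### AEs by severity (SAP Table 37) and by relationship (Table 38) are listed only for the DMF safety population, although the SAP makes the montelukast/placebo population primary

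*Combined protocol and SAP*

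**What the plan says.** **Populations.** SAP 7.1.2 defines two safety populations. One needs a dose of montelukast or placebo. The other needs only a dose of DMF. SAP 7.4.1 ranks them: "The primary safety analysis population is the Montelukast/placebo safety analysis population". SAP 7.1.2 and 7.2.1 agree, and leave the DMF population for selected outputs.

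**Table list (SAP Section 8).** Tables 33 to 36 (all AEs, SAEs, AEs leading to treatment discontinuation, AEs leading to withdrawal) each appear once per population. Table 37 appears once: "Incidence of adverse events by system organ class, preferred term and severity, DMF safety analysis population". So does Table 38: "Incidence of adverse events by system organ class, preferred term and by relationship to the study treatment or DMF, DMF safety population".

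**SAP text.** Section 7.4.2.1 plans a relationship summary without naming a population. It plans a severity summary only for AEs leading to discontinuation or withdrawal. It gives each population its own treatment-emergence rule, one starting from montelukast/placebo and the other from the first DMF dose.

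**Protocol.** Section 16.5.1 has a single safety population, based on DMF dosing. Section 16.5.2 plans all AEs by severity and by relationship. Section 7.1 expects that "approximately 295 subjects will be initially randomized to obtain approximately 118 subjects dosed with randomized study treatment", and adds: "Not all randomized subjects will be eligible to be dosed with randomized study treatment". Under Section 9.2, "eligible subjects will be randomized to 1 of 2 treatment arms (DMF + montelukast or DMF + placebo) in a 1:1 ratio".

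**The concern.** Severity and relatedness are the two breakdowns that show whether AEs on montelukast differ in kind from AEs on placebo. As listed, neither is shown in the population that took those treatments. Two features of the DMF population matter.

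- **Denominator.** Subjects who never reach the symptom threshold never take montelukast or placebo, so they cannot have an event caused by it. They still count in the DMF population.
- **Time window.** The DMF monitoring period lasts up to 28 days (protocol 7.2.4). Events in that time count as emergent in the DMF population although montelukast/placebo had not started. SAP 7.4.2.1 counts a subject with several AEs once, in the most related or worst-severity category. If that rule is applied to Table 37, a severe event on DMF alone could set a subject's category even though the later event on montelukast/placebo was mild. Flushing is a relevant example, because it is recorded on the CRF (protocol 15.2.1) and is a secondary endpoint.

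No other listed output fills the gap. Tables 33.1 to 36.1 are not split by severity or relationship. The listings in SAP Section 9 cover SAEs, discontinuations and withdrawals, deaths and laboratory values, but not all AEs.

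**Working it through.** **Inputs.** Planned randomized 295 and planned dosed 118, or 59 per arm (protocol 7.1); 1:1 allocation (protocol 9.2); enrollment to close at about 60 dosed (SAP Section 5).

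**The plan's own figure.** Dosed share = 118/295 = 40.0%, so the never-dosed share is 60.0%. The documents give no derivation of 295; it equals 118/0.40, which implies that 40% are expected to reach the threshold.

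**Dilution of montelukast/placebo-related events (Table 38).** Never-dosed subjects add to the denominator and nothing to the numerator. If they are pooled into the arm columns:

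- Denominator per arm = 295/2 = 147.5, against 59 dosed.
- Factor = 147.5/59 = 295/118 = 2.50.

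**Illustration (assumed counts).** Take six montelukast-arm and two placebo-arm subjects with an event judged related to montelukast/placebo.

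| | Dosed population | DMF population, pooled |
|---|---|---|
| Montelukast arm | 6/59 = 10.2% | 6/147.5 = 4.1% |
| Placebo arm | 2/59 = 3.4% | 2/147.5 = 1.4% |
| Difference | 6.8 points | 2.7 points |
| Ratio | 3.0 | 3.0 |

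Both arms are diluted about equally, so the ratio is roughly kept while absolute rates and differences shrink.

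**Sensitivity to the planning assumptions.**

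- Not all 295 take DMF, 118 still dosed (assumption). At 80%, 236/118 = 2.0, with 1 − 118/236 = 50% never dosed. At 95%, 280.25/118 = 2.4, with 58% never dosed.
- A different share reaches the threshold, all randomized subjects taking DMF (assumption). The factor is 1/share: 50% gives 2.0, 60% gives 1.7, 70% gives 1.4. A share below 40% would raise it above 2.5.
- Early closure. With 60 dosed and the same 40% share, 60/0.40 = 150 are randomized and 150/60 = 2.5. The factor depends on the share and not on the total.

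**Table 37, and DMF-related events in Table 38.** Here never-dosed subjects also contribute events. On planning figures the rate shown per arm is 0.4 × a + 0.6 × b, where a is the incidence from first DMF dose among dosed subjects and b the incidence among never-dosed subjects. The rate of interest is c, the incidence among dosed subjects emergent from montelukast/placebo. Because the DMF window contains the later one, a is at least c. The documents give no value for b. The rate shown can therefore lie above or below c.

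**The case against.** The strongest reply is that this is a mismatch between text and table list, and not a decision to leave the analysis out. SAP 7.2.1 and 7.4.1 set montelukast/placebo as the default, SAP 7.4.2.1 plans the relationship summary without restricting it, and Section 8 says that it lists the main tables and that more may follow. For relationship this stands: a reader might infer that the SAP plans the analysis only in the DMF population, and the text does not support that. It stands less well for severity, because the text covers only AEs leading to discontinuation or withdrawal, so the default does not clearly supply a table of all AEs. Permission to add tables also does not prespecify one.

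A second reply is that Tables 37 and 38 follow the protocol, whose only safety population is DMF-based and which plans both breakdowns. This stands as a reason to keep them. It does not explain why the SAP's own primary population has no counterpart when Tables 33 to 36 do.

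A third reply concerns size. A reader might infer that every rate in both tables is 2.5 times too low. The documents do not support that. The factor applies only to montelukast/placebo-related events in Table 38, it rests on planning figures, and the titles do not say whether never-dosed subjects would have their own column.

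Finally, a reader might infer that the safety comparison of the arms is missing. It is not. All AEs, SAEs and AEs leading to discontinuation or withdrawal are listed in the montelukast/placebo population (Tables 33.1 to 36.1), and flushing is compared by arm in the modified ITT population (SAP 7.3.4).

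**Conclusion.** The point holds as a gap in the table list. The severity and relationship tables are listed only in the supplementary safety population, against the SAP's own ranking and its own pairing of the other AE tables. Followed as listed, both would include events from before montelukast/placebo and subjects who never took either.

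The 2.5-fold dilution of montelukast/placebo-related rates in Table 38 rests on three assumptions: all 295 take DMF, 40% reach the threshold, and never-dosed subjects are pooled by arm. Relaxing either of the first two over the ranges shown gives factors from 1.4 to 2.4. A separate column for never-dosed subjects would remove the dilution. No direction can be claimed for Table 37 or for DMF-related events.

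No efficacy conclusion depends on this. It should still be corrected before the tables are produced, because the gap is specific and closing it costs little.

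**What to change.** 1. Add Tables 37.1 and 38.1 in the montelukast/placebo safety population, by arm, using the treatment-emergence rule that SAP 7.4.2.1 already gives for that population.
2. Keep the present DMF-population tables, renumbered 37.2 and 38.2, in line with the pairing of Tables 33 to 36 and with protocol 16.5.1.
3. Align the severity sentence in SAP 7.4.2.1, which covers only AEs leading to discontinuation or withdrawal, with Table 37 and with protocol 16.5.2, which covers all AEs.

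Cost: two more tables from existing programs and one edited sentence. No new data are needed.

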9 LIST OF LISTINGS

Listing 1: Listing of subjects who discontinued treatment and/or withdrew from study

Listing 2: Listing of serious adverse events

Listing 3: Listing of adverse events led to study withdrawal

Listing 4: Listing of death

Listing 5: Listing of out of normal range laboratory results

10 LIST OF FIGURES

Figure 1: Mean (SE) change in GSRS score from baseline (Day 0), by time and treatment group, Day 1 to Day 10

Figure 2: Model-based estimated mean change in GSRS score from baseline (Day 0), with 95% CI, by time and treatment group, Day 1 to Day 10

Figure 3: Kaplan-Meier plot for time to the first worsening of GSRS score from Day 0 GSRS score, by treatment group

Figure 4: Kaplan-Meier plot for time to recovery to Day 0 score from the last occurrence of worst GSRS score, by treatment group

Figure 5: Mean (SE) change in GSRS score from baseline (Day 0), by time and treatment group, Day 1 to Week 10

Figure 6: Model-based estimated mean change in GSRS score from Day 0, by time and treatment group, Day 1 to Week 10
